**11.5.3.6. BDI/TDI**

**BDI/TDI**

**General**

- The BDI focal score will be calculated as the sum of the ratings recorded for each of the three individual scales (Functional Impairment, Magnitude of Task, and Magnitude of Effort). Each of these scales has five possible scores ranging from 0 to 4 (with lower scores indicating more impairment), with the range of the BDI focal score 0 to 12. If a score is missing for any of the three scales, then the BDI focal score will be set to missing. BDI is assessed at baseline (Day 1).
- The TDI focal score will be calculated as the sum of the ratings recorded for each of the three individual scales (Functional Impairment, Magnitude of Task, and Magnitude of Effort). Each of these scales has a possible score ranging from -6 (major deterioration) to +6 (major improvement). TDI focal score is calculated as the sum of the three individual scores and then

BDI/TDI

divided by 2 (so the range of the TDI focal score is -9 to +9). If a score is missing for any of the three scales, then the TDI focal score will be set to missing.
 
 
• If the language of the TDI conducted at a visit is different to the language for the BDI, all TDI scores at that visit and subsequent visits will be set to missing.
 
• If there is more than one response to a question at a visit or duplicate questionnaires, the BDI or TDI score for that visit will be set to missing.
 

Categorization of TDI Focal Score

 
• Full categorization of TDI focal score for categorical summary is as follows: 
 
‘major improvement’ defined as a score of <math>\geq 7</math> to <math>\leq 9</math>
 
‘moderate improvement’ defined as a score of <math>\geq 4</math> to <math>< 7</math>
 
‘minor improvement’ defined as a score of <math>\geq 1</math> to <math>< 4</math>
 
‘no change’ defined as a score of <math>> -1</math> to <math>< 1</math>
 
‘minor deterioration’ defined as a score of <math>> -4</math> to <math>\leq -1</math>,
 
‘moderate deterioration’ defined as a score of <math>> -7</math> to <math>\leq -4</math>
 
‘major deterioration’ defined as a score of <math>\geq -9</math> to <math>\leq -7</math>
 
 
 

Responder Status according to TDI Focal Score

 
• A subject will be considered a responder if the on-treatment TDI focal score was at least 1 unit.
 
• A subject will be considered a non-responder if their on-treatment TDI focal score was less than 1 unit.
 
• Missing data will be handled as detailed in Section 11.6.
 
• For subjects who are responders at a particular visit, response will be further classified as moderate if the TDI focal score is <math>\geq 4</math> and <math>< 7</math> and as major if the TDI focal score is <math>\geq 7</math>.
 

**11.5.3.7. eDiary**

Calculation of Daily eDiary Endpoints
General

 
• Subjects were instructed to complete the daily eDiary in the morning prior to taking any study treatment.
 
• Number of occasions of rescue salbutamol use and number of nighttime awakenings were collected in the daily eDiary.
 
• The Yes/No question of “Did your respiratory symptoms stop you performing your usual activities in the last 24 hours?” were also collected in the eDiary.
 
• The table below shows which daily eDiary records are used to calculate the daily eDiary endpoints for each analysis time period. Any diary data collected in the post-treatment phase of the study will not be slotted. See Section 11.3.3 for details on the assignment of treatment phases.
 

Calculation of Daily eDiary Endpoints		
Daily Record		Analysis Time Period
Beginning Timepoint (day)	Ending Timepoint (day)	
-13	1	Week -1 (Baseline)
2	29	Weeks 1 – 4
30	57	Weeks 5 – 8
58	85	Weeks 9 – 12
86	113	Weeks 13 – 16
114	141	Weeks 17 – 20
142	169	Weeks 21 – 24
170	197	Weeks 25 – 28
198	225	Weeks 29 – 32
226	253	Weeks 33 – 36
254	281	Weeks 37 – 40
282	309	Weeks 41 – 44
310	337	Weeks 45 – 48
338	365	Weeks 49 – 52

Note: There is no Day 0. Any records with actual day>365 will not be assigned to a time period.

Note: Daily eDiary records that were not assigned to a time period will not be used in calculation of daily eDiary endpoints.

- For a subject to be counted in any time period (except for baseline where at least 7 days non-missing entries are required) for a given endpoint they must have at least one diary entry recorded for that endpoint during that time period.
- Any daily eDiary data that were collected post-study treatment discontinuation will be excluded from analysis, including four weekly period data summaries.
- If a subject has more than one daily eDiary record for any given day, the worst case response on that day for each endpoint will be used in the summaries and analyses. i.e. the maximum number of occasions of rescue use reported will be counted for the day in question and used to determine if it was a rescue-free day; the maximum number of nighttime awakenings will be counted for the day in question; symptoms stopped usual activities = 'Yes' will be used as the worst case over symptoms stopped usual activities = 'No'.

**eDiary Endpoints**

- The mean number of occasions of rescue use per day, percentage of rescue-free days, mean number of nighttime awakenings per night and percentage of days symptoms stopped usual activities will be calculated for each subject during the four weekly periods defined above.

**11.5.3.8. EQ-5D-5L**

EQ-5D-5L

 
• If the language of the EQ-5D-5L conducted at a post-baseline visit is different to the language used at baseline, the EQ-5D-5L scores for that visit and all subsequent visits will be set to
 

missing.

- If there is more than one response to a question at a visit or duplicate questionnaires, the EQ-5D-5L health state and utility score for that visit will be set to missing.

**11.5.3.9. Healthcare Resource Utilization**

**Healthcare Resource Utilization**

- The total number of visits for each type of healthcare contact (home visits (day), home visits (night), office/practice visits, urgent care/outpatient clinic visits, emergency room visits) and number of days in intensive care and number of days in general hospital wards will be calculated by summing the respective visits and number of days. This will also be calculated for each contact type (COPD exacerbations, COPD not-exacerbation, other healthcare contact).

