8.3.5.3. Health Outcomes Analyses

Details of the analysis of all health care utilization endpoints will be specified in the RAP.

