Secondary Endpoints and Treatment Comparisons	
 
Change from baseline in trough forced expiratory volume in 1 second (FEV1) at Week 52 comparing FF/UMEC/VI with FF/VI
 
Change from baseline in St. George's Respiratory Questionnaire (SGRQ) Total Score at Week 52 comparing FF/UMEC/VI with FF/VI
 
Time to first on-treatment moderate/severe exacerbation comparing FF/UMEC/VI with FF/VI and with UMEC/VI
 
Annual rate of on-treatment moderate/severe exacerbations comparing FF/UMEC/VI with UMEC/VI in the subset of subjects with a blood
 

Overview	Key Elements of the RAP
	
eosinophil count <math>\geq 0.15 \times 10^9/L</math>
 
 
• Time to first on-treatment moderate/severe exacerbation comparing FF/UMEC/VI with UMEC/VI in the subset of subjects with a blood eosinophil count <math>\geq 0.15 \times 10^9/L</math>
 
• Annual rate of on-treatment severe exacerbations comparing FF/UMEC/VI with FF/VI and with UMEC/VI
 

Study Design	
 
• This is a phase IIIa, randomized, double-blind, 3-arm parallel group, global multicenter study evaluating FF/UMEC/VI (100/62.5/25 mcg) inhalation powder versus FF/VI (100/25 mcg) inhalation powder and UMEC/VI (62.5/25 mcg) inhalation powder all given once daily in the morning. The target enrollment is 10,000 randomized subjects at approximately 1,000 study centers globally.
 
• Eligible subjects will be randomized (2:2:1) to one of the following double-blind treatment groups: 
 
• FF/UMEC/VI 100/62.5/25 mcg (n=4,000)
 
• FF/VI 100/25 mcg (n=4,000)
 
• UMEC/VI 62.5/25 mcg (n=2,000)
 
 
 
• The total duration of subject participation will be approximately 55 weeks, consisting of a 2-week run-in period, up to 52-week treatment period and a 1-week safety follow-up period.
 
• Subjects who have permanently discontinued study treatment are not required to withdraw from the study. Subjects who have permanently discontinued study treatment and have not withdrawn consent may continue in the study and complete all remaining protocol specified visits by telephone contact to collect exacerbations, SAEs and concomitant medications. This off-treatment data will be used in sensitivity analyses for assessing the effect of missing data on study conclusions.
 

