**9.1.1.8.     Unscheduled Healthcare Resource Utilization**

Summaries of all-cause unscheduled healthcare resource utilization will be provided for the on-treatment period for the ITT population. This will be repeated by contact type.

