
 
● All data (including data collected post-study treatment discontinuation) will be reported according to the treatment to which the subject was randomized unless otherwise stated. However, there may be additional adhoc displays for individual subjects using the actual treatment received.
 
● GSK IDSL Statistical Principles (5.03 & 6.06.3) for decimal places will be adopted for reporting of eCRF data based on the raw data collected.
 
● The reported precision from non eCRF sources will follow the IDSL statistical principles but may be adjusted to a clinically interpretable number of decimal places.
 
● Summaries of continuous data will include number of subjects, mean, standard deviation, median, first quartile, third quartile, minimum and maximum,
 
● Percentages between 1% and 99%, inclusive, will be rounded to integers. Percentages greater than 0%, but less than 1%, will be reported as <1%, and percentages greater than 99%, but less than 100%, will be reported as >99%.
 
● Numeric data will be reported at the precision collected in the eCRF.
 
	
Planned and Actual Time	

 
● Reporting for tables, figures and statistical analyses: 
 
○ Planned time relative to dosing will be used in figures, summaries, statistical analyses and calculation of any derived parameters, unless otherwise stated. Actual time will be used for calculation of times to events and Kaplan-Meier plots.
 
 
 
● Reporting for listings: 
 
○ Planned and actual time relative to study treatment dosing will be shown in listings (refer to IDSL Statistical Principle 5.05.1).
 
 
 
	
Unscheduled Visits	

 
● Unscheduled visits will not be included in summary tables except as part of a maximum/minimum/worst case post-baseline assessment or if they are assigned as the baseline assessment as detailed in Section 11.4.2.
 
● All unscheduled visits/unplanned readings will be included in listings.
 
	
Cardiovascular Event Reports	

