**11.5.3. Efficacy and Health Outcomes**

**11.5.3.1. Exacerbations**

COPD Exacerbations
General

 
● Each COPD exacerbation will be categorized based on severity as follows: 
 
○ Mild: no treatment with systemic/oral corticosteroids and/or antibiotics and no hospitalization and that did not result in death
 
○ Moderate: required treatment with systemic/oral corticosteroids and/or antibiotics (not involving hospitalization or resulting in death)
 
○ Severe: required hospitalization or resulted in death
 
 
 
● The duration of an exacerbation will be calculated as exacerbation resolution date or date of death - exacerbation onset date + 1.
 
● Summaries of moderate/severe exacerbations by treatment course are defined as exacerbations treated with systemic/oral corticosteroids (with or without antibiotics), and exacerbations treated with antibiotics (with or without systemic/oral corticosteroids).
 
● The raw event rate per thousand subject-years for exacerbations will be calculated as the number of events x 1000 divided by the at risk period during the time-period of interest as defined in Section 11.5.1.5.2
 
● For the boxplot of on-treatment moderate/severe annual raw COPD exacerbation rates the individual subject rate will be derived as number of events experienced by the subject x 1000 divided by the individual subject's on-treatment at risk period as defined in Section 11.5.1.5.2.
 

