**11.5.4.2. Adverse Events**

**Adverse Events**

**Adverse Event Rate**

- The event rate per thousand subject-years will be displayed on most AE data displays listed in Section 11.12 (including summaries of AESIs and Serious Adverse Reports). Event rate per thousand subject-years will be calculated as the number of events x 1000 divided by the at risk period during the time-period of interest as defined in Section 11.5.1.5.2.

Adverse Events of Special Interest (AESI)		

 
AESI have been defined as AEs which have specified areas of interest for FF, VI or UMEC or the overall COPD population. The following table presents the AESI groups. Groups which are not SMQs are made up of a selection of preferred terms (PTs) defined by GSK. The complete list, including the PTs which contribute to each of the groups will be provided by Global Clinical Safety and Pharmacovigilance (GCSP) using the MedDRA version current at the time of reporting. This will be finalized prior to unblinding.
 
		
AESI Group	AESI Subgroup	Sub-SMQ
Adrenal suppression		
Anticholinergic syndrome (SMQ)		
Asthma/bronchospasm (SMQ)		
Cardiovascular effects	Cardiac arrhythmia	Arrhythmia related investigations, signs and symptoms (SMQ)
		Bradycardia terms, nonspecific (SMQ)
		Conduction defects (SMQ)
		Disorders of sinus node function (SMQ)
		Cardiac arrhythmia terms, nonspecific (SMQ)
		Supraventricular tachyarrhythmias (SMQ)
		Tachyarrhythmia terms, nonspecific (SMQ)
		Ventricular tachyarrhythmias (SMQ)
	Cardiac failure (SMQ)	
	Ischaemic heart disease (SMQ)	
Hypertension (SMQ)		
Central nervous system haemorrhages and cerebrovascular conditions (SMQ)		
Ocular effects	Glaucoma (SMQ)	
	Lens disorder (SMQ)	
Decreased bone mineral density and associated fractures		
Effects on potassium		
Gastrointestinal obstruction (SMQ)		
Hyperglycaemia/new onset diabetes mellitus (SMQ)		
Hypersensitivity		
Local steroid effects		
Pneumonia		
Lower Respiratory Tract Infection (LRTI) excluding pneumonia		
Tremor		
Urinary retention		

Adverse Events Considered of Interest in the Elderly	

 
• AEs considered of interest in the elderly will be summarized by age category and overall for each treatment group.
 
• SMQs or PTs for these groupings are provided below.
 
	
AE Grouping	SMQ, PT or System Organ Class (SOC)
Any AE	
Serious AE	
Results in death	
Life-threatening	

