2.085	ITT	Summary of On-treatment Adjudicated Cause of Death by Eosinophil Subgroup	SAC
2.086	ITT	Summary of Adjudicated Cause of Death Including Off-treatment Data	SAC
2.087	ITT	Summary of Adjudicated Cause of Death Including Off-treatment Data by Eosinophil Subgroup	SAC
2.088	ITT	Summary and Analysis of Time to On-treatment All Cause Mortality	SAC
2.089	ITT	Summary and Analysis of Time to All Cause Mortality Including Off-treatment Data	SAC
CAT			
2.090	ITT	Summary of Baseline CAT Score	SAC
2.091	ITT	Summary of Baseline CAT Score by Eosinophil Subgroup	SAC
2.092	ITT	Summary of CAT Score	SAC
2.093	ITT	Summary of CAT Score by Eosinophil Subgroup	SAC
2.094	ITT	Analysis of CAT Score	SAC
2.095	ITT	Analysis of CAT Score by Eosinophil Subgroup	SAC
2.096	ITT	Summary and Analysis of Proportion of Responders According to CAT Score	SAC
2.097	ITT	Summary and Analysis of Proportion of Responders According to CAT Score by Eosinophil Subgroup	SAC
Subject Global Ratings			
2.098	ITT	Summary of Subject Global Rating of Activity Limitation	SAC
2.099	ITT	Summary and Analysis of Subject Global Rating of Change in Activity Limitation	SAC
2.100	ITT	Summary of Subject Global Rating of COPD Severity	SAC
2.101	ITT	Summary and Analysis of Subject Global Rating of Change in COPD Severity	SAC
Daily Diary Assessments			
2.102	ITT	Summary of Mean Number of Occasions of Rescue Use per Day	SAC
2.103	ITT	Analysis of Mean Number of Occasions of Rescue Use per Day by Four Weekly Period	SAC
2.104	ITT	Summary of Percentage of Rescue-Free Days	SAC
2.105	ITT	Analysis of Percentage of Rescue-Free Days by Four Weekly Period	SAC
2.106	ITT	Summary of Mean Number of Nighttime Awakenings per Night	SAC
2.107	ITT	Analysis of Mean Number of Nighttime Awakenings per Night by Four Weekly Period	SAC
2.108	ITT	Summary of Percentage of Days Symptoms Stopped Usual Activities	SAC
2.109	ITT	Analysis of Percentage of Days Symptoms Stopped Usual Activities by Four Weekly Period	SAC
EQ-5D-5L			
2.110	ITT	Summary of EQ-5D-5L VAS Scores	SAC
2.111	ITT	Summary of EQ-5D-5L Utility Indices	SAC

Efficacy: Tables			
No.	Population	Title	Deliverable [Priority]
Healthcare Resource Utilization			
2.112	ITT	Summary of Unscheduled Healthcare Resource Utilization	SAC
2.113	ITT	Summary of Unscheduled Healthcare Resource Utilization by Contact Type	SAC

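### Unscheduled healthcare resource use is summed over the on-treatment period with no time-at-risk denominator, so arm comparisons depend on time on treatment if discontinuation differs

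*SAP*

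**What the plan says.** The protocol names healthcare utilisation, all-cause and COPD-related, as a health outcome endpoint and leaves its analysis to the SAP: "Details of the analysis of all health care utilization endpoints will be specified in the RAP" (Protocol 8.3.5.3).

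The SAP covers it in three places:

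- **Period and population (9.1.1.8).** "Summaries of all-cause unscheduled healthcare resource utilization will be provided for the on-treatment period for the ITT population", repeated by contact type.
- **Derivation (11.5.3.9).** The number of visits of each kind, and the days in intensive care and on general wards, "will be calculated by summing the respective visits and number of days". The same is done for COPD exacerbation contacts, other COPD contacts and other contacts.
- **Displays (Table 5 and 11.12.5).** There are summary tables only, numbered 2.112 and 2.113. The second is titled "Summary of Unscheduled Healthcare Resource Utilization by Contact Type". Neither title mentions a rate.

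The SAP does not say whether totals are shown per subject or per arm. The general convention in 11.4.3 ("Summaries of continuous data will include number of subjects, mean, standard deviation, median") suggests per-subject statistics.

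Other count data in the SAP are treated differently. Exacerbations are reported as the "number of events x 1000 divided by the at risk period during the time-period of interest" (11.5.3.1). For adverse events, "Event rate per thousand subject-years will be calculated as the number of events x 1000 divided by the at risk period" (11.5.4.2). Deaths (11.5.3.5) also have an at-risk denominator, and fractures, ECG abnormalities, pneumonia and MACE follow the adverse event method (11.5.4.3, 11.5.4.6, 11.5.4.7, 11.5.4.9).

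**The concern.** A subject who stops treatment early has less time in which to record an on-treatment contact. The gap cannot be filled from later data. Resource use is scheduled at Visits 3 to 7 and the IP Discontinuation Visit (Protocol Table 4). After that, subjects who remain in the study "complete all remaining protocol specified visits by telephone contact to collect exacerbations, SAEs and concomitant medications" (SAP section 1), and resource use is not on that list. Each subject's count therefore ends at about the time treatment ends.

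Unequal discontinuation is plausible in this trial. The arms are hypothesised to differ in efficacy, lack of efficacy is a listed reason for stopping (Protocol 4.4.4), and the SAP plans Kaplan-Meier plots of discontinuation by arm and a sensitivity analysis that counts discontinuation as an event (8.3.2.2). If the less effective arm loses more time on treatment, its totals shrink relative to the others and a true saving with the better-retained arm looks smaller than it is.

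The SAP would also be inconsistent within itself. A COPD admission counted as a severe exacerbation is divided by time at risk, while the ward days from that same admission are not.

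**Working it through.** The documents state no rate, effect size or discontinuation proportion for this endpoint, so there is no planned figure to reproduce. The discontinuation inputs below are assumptions, used to show a range.

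**Set-up.** Let *d* be the share of an arm that stops early and *f* the mean fraction of the 52 weeks completed by those who stop. Mean time on treatment, as a fraction of the year, is

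*T* = 1 - *d*(1 - *f*).

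The expected raw total per subject is the contact rate times *T*. With equal true rates, the ratio of raw totals (worse-retained arm over better-retained arm) equals the ratio of the two values of *T*.

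| *d*, better / worse | *f* | *T*, better | *T*, worse | Ratio of raw totals |
|---|---|---|---|---|
| 15% / 20% | 0.5 | 0.925 | 0.900 | 0.973 |
| 15% / 20% | 0.4 | 0.910 | 0.880 | 0.967 |
| 18% / 25% | 0.5 | 0.910 | 0.875 | 0.962 |
| 18% / 25% | 0.4 | 0.892 | 0.850 | 0.953 |
| 18% / 30% | 0.5 | 0.910 | 0.850 | 0.934 |
| 18% / 30% | 0.4 | 0.892 | 0.820 | 0.919 |

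The understatement runs from 2.7% to 8.1%. If *d* and *f* are the same in both arms, the ratio is 1.00 and there is no distortion.

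**Effect on a true difference.** The only effect sizes in the documents are the targeted reductions in moderate and severe exacerbations, 12% and 15% (Protocol 8.2.1). They are a scale only, because Table 2.112 is all-cause. Those reductions correspond to comparator ratios of 1/0.88 = 1.136 and 1/0.85 = 1.176.

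- Smallest distortion (0.973): these appear as 1.11 and 1.14.
- Largest distortion (0.919): these appear as 1.04 and 1.08.

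The difference is reduced and keeps its direction. To be cancelled, the true excess would have to be 0.925/0.900 - 1 = 2.8% at the small end or 0.892/0.820 - 1 = 8.8% at the large end; anything smaller would be reversed.

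**A more extreme assumption.** With 10% against 30% stopping at mid-year, the ratio is 0.850/0.950 = 0.895, and a true ratio of 1.12 would appear as 1.00. That takes a 20-point gap in discontinuation, for which the documents give no basis.

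**After the fix.** Dividing total contacts by total on-treatment time gives (rate × *T*)/*T* = rate, so the ratio is 1.00 in every equal-rate scenario above.

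**The case against.** The strongest reply is that little depends on these tables. Resource use has no model, no p-value and no place in the testing hierarchy, and neither table is a first-priority deliverable. That stands, and it limits the point to the reporting of a descriptive health outcome.

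A second reply is that major drivers of resource use are already analysed with time at risk. Severe exacerbations use negative binomial regression with a log-time offset (SAP 8.5, 11.5.3.1). Pneumonia and cardiovascular events leading to hospitalisation or death use censored Cox models (SAP 9.2.13.2). Exposure is tabulated by arm (Tables 3.001 to 3.006), so a reader could form a crude rate from arm totals or means. This is a partial safeguard. It does not cover outpatient, urgent care or home contacts, and a reader's crude rate is not a pre-specified one.

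Third, 11.5.3.9 is a derivation rule, and nothing in it forbids a rate in the tables. That is true. But the SAP writes out the rate for the other event counts listed above, and here it does not, so the plain reading is that none is planned.

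A reader might go further and infer that the worse-retained arm will appear to have used fewer resources, or that a true saving would be hidden or reversed. The documents do not support this. They give no discontinuation by arm, so neither the size nor the direction of any bias is known. A true excess larger than the distortion would still show as an excess, and the 3-8% range only attenuates differences of the 12-15% order.

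**Conclusion.** The gap is real and modest. As written, comparisons of resource use between arms depend on time on treatment as well as on the rate of use, unlike the other event counts in the same SAP. If discontinuation differs, the arm with less time on treatment shows use below its true rate relative to the other, by about 3-8% under the assumed proportions and timing, and by nothing if discontinuation and its timing are equal. This would attenuate a true difference and could mask one only if it were of similarly small size. No primary or secondary conclusion is affected. The size rests wholly on assumed discontinuation; the absence of a denominator rests on the text.

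**What to change.** In SAP 11.5.3.9 and Tables 2.112 and 2.113, add contacts and intensive care and ward days per 1,000 subject-years beside the raw counts, overall and by contact type, using the on-treatment at-risk period of 11.5.1.5.2.

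State a counting rule for hospital days. The SAP assigns events to a phase by onset date (11.3.3), while the at-risk period ends no later than the day after treatment stops. If resource use followed the onset rule, a stay that began on treatment would contribute all its days to a denominator that had already closed. Counting only days within the at-risk period keeps numerator and denominator matched.

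No new data or model is needed, and the denominator is already defined, so the cost is slightly more programming. Setting the rule before unblinding avoids a post hoc choice of denominator. An on-treatment rate removes the mechanical effect of shorter exposure but leaves any bias from informative discontinuation, which the table footnote should say.
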